**Neuromodulatory Treatments for Pain Management in Veterans With Complex TBI
Using Mobile Technology**

NCT03418129

Document Date: December 5, 2022

Purpose of the Study

Aim 1: Examine the effectiveness of mobile interventions for reducing pain symptoms in Veterans with complex TBI. Hypothesis 1: Given preliminary data and empirical support for neurofeedback and mindfulness, we hypothesize that Veterans in the two intervention groups will report less pain at 3 months compared to Veterans in the control group.

Aim 2: Investigate the impact of neurofeedback and mindfulness on brainwave activity in Veterans with complex TBI and chronic pain. Hypothesis 2: Given research on electroencephalogram (EEG) and pain, we hypothesize that Veterans in the two intervention groups will show increased (8–12 Hz) alpha power at 3 months compared to Veterans in the control group.

Given connections to adverse outcomes, we will explore whether neuromodulatory interventions impact: (i) risk behaviors, with a hypothesis of lower levels of suicidality, aggressiveness/ violence toward others, and use of alcohol and drugs for the neurofeedback and mindfulness groups compared to the control group; and (ii) heart rate variability (HRV), with a hypothesis of significantly greater improvements in HRV compared Veterans to the control group.

Background & Significance

Traumatic brain injury (TBI) and chronic pain are common and serious health problems for Veterans of Operations Enduring Freedom, Iraqi Freedom, and New Dawn (OEF/OIF/OND) and often co-occur, leading to poor post-deployment adjustment. Pharmacological treatments for pain elevate risk of opioid abuse, and research suggests veterans perceive barriers to existing non-pharmacological, clinic-based treatments.

Thus, there is an urgent need to develop pain management approaches that are effective, overcome barriers to care, and are readily usable by Veterans. Evidence suggests that two neuromodulatory treatments, neurofeedback and mindfulness, reduce pain-related symptoms, are grounded in understanding of neurophysiological mechanisms of pain, and have the potential to be developed into self-implemented treatments through use of mobile technology. Preliminary data from our research team shows feasibility and benefit of mobile neurofeedback for pain management among Veterans with complex TBI, including data suggesting decreased emotional dysregulation and pain intensity immediately after using mobile neurofeedback. Similarly, studies show that mindfulness can be used outside the clinic and on mobile apps, but to our knowledge, no research has evaluated using mindfulness on mobile devices for pain management.

Design & Procedures

This study is a prospective, three-arm, randomized controlled trial of neuromodulatory treatments for chronic pain, enrolling 300 post-9/11 veterans with co-occurring pain and TBI. Participants will be scheduled for a baseline interview at [name] research office at Duke or via WebEx/Zoom after

passing a preliminary telephone screen. All contact information for individuals who are identified as potential participants will be destroyed if they refuse or are ineligible to participate in the study, except for names. To avoid duplicate screens, we will keep a separate list of names only of all people who have been screened or refused to participate. No other sensitive information will be recorded in that document.

After providing informed consent, participants will complete an assessment including clinical interviews for TBI, chronic pain, and cognitive function; self-report instruments measuring chronic pain, TBI outcomes, suicidality, violence/aggression, drug and alcohol use, mental health, demographics, military experience, behavioral activation (BADS-SF) and medications/treatment, and an EEG/ECG reading. Participants will be assigned to one of three groups (n=100 in each): neurofeedback [using a (Muse) portable EEG headset and Mobile Muse: the brain sensing headband Neurofeedback app created by our group], mindfulness (using a mindfulness app created by our group, derived from the DoD and VA Mindfulness Coach app), or unstructured relaxation/control (using a relaxation app, also created in-house). All participants will receive an iPod Touch, be trained to use their respective app and instructed to practice 10 minutes a day, 4 times a week for 12 weeks, and be set up to receive reminders to practice from their iPod Touch or smartphone calendars. If participants prefer to receive reminders on their smartphone, they will be instructed to add a reminder in the calendar app on their smartphone that reminds them to complete their 10-minute practice sessions 4 times per week. Participants will be asked to report their current level of pain, stress, and anger before and after each session. Study coordinators will conduct two home visits (week 1 and week 6) and two phone calls (week 3 and week 9) to reinforce training, troubleshoot difficulties, observe participants utilizing the intervention in their home environment, and collect data on usability and tolerability. Follow-up data will be collected upon completion of the intervention at 12 weeks and again at 24 weeks. During both follow-up visits, veterans will complete clinical interview, pain assessment, self-report instruments including current traditional and alternative pain treatments, and EEG/ECG reading. Due to COVID-19, some participants will be asked to complete visits remotely. Coordinators will conduct "home visit" phone calls and will conduct baseline (screening/enrollment) follow-up interviews over the phone or via WebEx/Zoom, as needed. During these visits, there will be no EEG or HRV readings or cognitive testing. Data will be downloaded from the iPods once they are shipped back to our Duke offices following the participants' completion of the intervention at 3 months. For remote follow-up visits, participants will complete part of the visit over the phone and/or WebEx/Zoom, emailed a Qualtrics link to complete survey questionnaires, and emailed a FedEx label for shipping study equipment. Intervention Training will be combined with Home Visit 1 for remote visits, and we will follow up with a short phone call ~1 week later to assess for adverse events and safety measures. We will also ask two home visit questions, "Can you give any examples of specific times or situations in which the intervention was helpful?" and "What problems, if any, have you had using the app since you last talked with us?"

Selection of Subjects

Inclusion criteria:

- 18 years of age or older
- Served in one of the military branches (Army, Navy, Marines, Air Force, or Coast Guard) in OEF

/OIF/OND (since October 2001)

-Meets DoD criteria for diagnosis of a TBI, defined as a traumatically induced structural injury or physiological disruption of brain function, as a result of an external force, that is indicated by new onset or worsening of at least one of the following clinical signs immediately following the event:

- Any alteration in mental status (e.g., confusion, disorientation, slowed thinking, etc.).
- Any loss of memory for events immediately before or after the injury.
- Any period of loss or a decreased level of consciousness, observed or self-reported.
- External forces may include any of the following events: the head being struck by an object, the brain undergoing an acceleration/deceleration movement without direct external trauma to the head, or forces generated from events such as a blast or explosion, including penetrating injuries.

-Reports chronic musculoskeletal and/or neuropathic pain, defined as moderate or severe pain (≥ 4 on a 0-10 rating scale) in one or more body regions for the previous 3 months or more.

-For individuals on pain medication, inclusion criteria are that (a) their pain medication regimen has been stable for the past 4 weeks, (b) they do not expect any major changes in their pain medication regimen for the duration of the study, and (c) they do not expect to have surgery or to be hospitalized for pain treatment for the duration of the study.

Exclusion criteria:

-History of epilepsy, seizure disorder, or any seizure or epileptic fit.

-Individuals with implanted medical devices that could experience interference during EEG and /or ECG, such as a spinal cord stimulator or pacemaker.

-Unable to provide informed consent.

-Note: For remote visits, participants must have access to the internet. Thus, any potential participant who is eligible but does not have internet access will be deferred until they can be seen in the office.

-Participants outside of the state of North Carolina will be permitted to participate in the study remotely since there are currently no in-person requirements for study visits.

Subject Recruitment and Compensation

Participants will be recruited using a multi-pronged approach, including distribution of IRB approved flyers and email scripts at the Durham VA Medical Center and through veteran organizations, community organizations, universities and colleges, medical and outpatient centers in North Carolina, and local businesses/community spaces, as well as through targeted Facebook ads and posts.

Individuals interested in the study can self-identify by using the contact information to speak with a study coordinator. Participants may also follow a link to a REDCap survey (disseminated via social media ad/post, study flyer via a QR code, at recruitment events, and on the lab webpage), fill in their contact information, and request that a study coordinator contact them for a phone screen.

Participants will also be recruited through research registries of individuals who have consented to be contacted about research studies including the Duke Behavioral Health and Technology Lab Data Repository (Pro00076336) and the Durham VA Mental Illness, Research Education, and Clinical Center (MIRECC).

We will also identify participants using the tools available in Maestro Care to help identify and recruit potential participants before consent is signed. Only key personnel who are delegated the task of patient identification/ recruitment will have access to report information in Maestro Care. Participants will receive a MyChart message, and study staff will contact them for a phone screen.

Participants who complete the study remotely will not be excluded based on geographic location since there is currently no requirement for in-person visits.

Up to 400 participants will be consented, for a total of 300 participants randomized to treatment arms. Participants will be compensated \$100 for each in-office interview session, up to a total of \$300. Participants traveling from outside the Triangle (≥ 30 miles) will be given the Duke rate per mile traveled for in-office interview sessions, up to a total of \$100 per interview. For remote 3 month follow-up visits, in lieu of travel reimbursement, we will compensate participants \$35 for returning their study equipment, to for the time and travel required to ship materials back to us. Participants will be allowed to keep the iPod Touch they used during the study after completion. Participants who do not complete the study will be asked to return the iPod.

Study Interventions

Neurofeedback: The proposed study intervention for the neurofeedback group involves two components, the Muse portable EEG headset and the 'Mobile Neurofeedback' app. Study participants engage in neurofeedback to practice meditation and induce relaxation, with the goal of reducing pain symptoms. Participants will be given a mobile neurofeedback headset, the Muse, which connects to the 'Mobile Neurofeedback' app via Bluetooth. During a 'Mobile Neurofeedback' session, individuals receive continuous neurofeedback, rewarding them whenever EEG signals move into patterns of brain activity that indicate a calm, relaxed state. Using 'Mobile Neurofeedback,' participants can select a soothing sound to help them gauge how relaxed they are and track neurofeedback progress. Participants will be instructed to use Muse + 'Mobile Neurofeedback' a total of 10 minutes a day, 4 times a week for 12 weeks.

Mindfulness Training: The study intervention for the mindfulness group uses a Mindfulness app created by our study team, derived from the "Mindfulness Coach" app, which was created by the Department of Defense's National Center for Telehealth and Technology in partnership with the Department of Veterans Affairs National Center for PTSD. The app was modified to function and appear aesthetically similar to the Mobile Neurofeedback app. This app enables individuals to practice the foundational features of mindfulness, which as described above, has been shown in other contexts to be effective for reducing stress, improving emotional balance, increasing self-awareness, helping with anxiety and depression, and coping more effectively with chronic pain. Using an iPod Touch received at their initial study visit, individuals will perform the app's Mindful Breathing and Body Scan exercises. The Mindful Breathing exercise guides users to focus their attention on their breath, to non-judgmentally notice when they become distracted, and to then direct their attention back to their breath. The Body Scan exercise guides participants to direct their attention to different parts of their body, noticing the sensations they feel without judging or trying to change them. These have both been adapted into 10-minute audio-guided exercises with step-by-step instructions. Participants will also have the opportunity to select a relaxing musical or

ambient background sound, identical to the choices in the Mobile Neurofeedback app, which will play in the background of the guided exercises. Participants will be instructed to complete these sessions 4 times a week for 12 weeks.

Unstructured Relaxation (control group): The control group will use a Relaxation app, which is designed to promote relaxation. The Relaxation app, also created by our study team, is aesthetically similar to the Mobile Neurofeedback app and offers the same relaxing background sounds with nature images. To create the most relaxing experience, users can choose a background sound and adjust the volume. Sessions are set for 10 minutes, and participants will be instructed to complete these sessions 4 times a week for 12 weeks.

All participants will be asked to report pain, anger, and stress symptoms before and after each session. All apps include their own logging systems to track usage. Research staff will also directly collect this weekly app usage data from participants' iPods a total of six times (at the two home visits, the two phone calls, and at the 3 and 6-month follow-up visits) during the study period. Devices will be labeled according to FDA requirements for non-significant risk devices. To preserve blinding to study condition, the same label will be used on all devices and will include the most significant side effects possible from any of the interventions.

Risk/Benefit Assessment

We believe that this study poses minimal risk to participants and that the risk-to-benefit ratio in the proposed study is acceptable. Anticipated risks related to neurofeedback include drowsiness after neurofeedback practice sessions and minor discomfort due to practicing neurofeedback. There is also the chance that participants may experience headaches, dizziness, fatigue, tingling sensations, negative feelings such as anxiety or frustration, or increased risk of seizures among individuals with epilepsy or seizure disorder, although these side effects are rare. To minimize these risks, participants with a history of seizures will be excluded, and all participants will be instructed to practice neurofeedback at a time when they will not need to perform tasks that require high levels of alertness, such as driving or operating machinery. Participants are warned about each side effect prior to enrolling in the study and reminded again during neurofeedback training. Veterans will be asked if they have experienced any side effects during each scheduled study interaction and are instructed to contact research staff if they experience any of these adverse effects in conjunction with using the neurofeedback. Participants are instructed to discontinue use of neurofeedback if any of these adverse effects begins to affect their daily activities.

Mindfulness training or the control relaxation condition do not present a potential for serious risk to the health, safety, or welfare of a subject. It is possible that the process of learning mindful awareness may temporarily increase feelings of discomfort due to increased awareness. Veterans in the mindfulness and relaxing sounds groups will be instructed to discontinue the intervention if they experience any previously unknown adverse effects, to seek medical assistance if they require it, and to report the adverse effects to the researchers.

It is possible that some participants may become upset by interview questions, i.e., in response to

questions that ask about sensitive personal information or traumatic experiences. Participants will be made aware of what to expect during study procedures prior to their participation, and they will be informed in the consent form that the procedures may potentially lead to more distress. Participants will also be informed that they may discontinue their participation at any time. Interviews will be conducted by research staff trained in interviewing and de-escalation. Veterans who become upset during the interview will be informed that they need not complete the interview and that our staff can make arrangements for them to see a clinician at the mental health center. Finally, there is a risk of breach of confidentiality associated with any research. See section 14 below regarding steps to minimize the risk of breach of confidentiality.

This study advances the field by testing the efficacy of portable, technology-based neuromodulatory approaches by permitting Veterans to manage pain in a self-directed manner outside a clinic setting. This project will be the first to test the efficacy of such interventions in a population of Veterans reporting frequent and intense chronic pain, namely, post-9/11 Veterans with complex TBI. If we find that neurofeedback or mindfulness delivered via mobile technology is effective in reducing pain, our research team is uniquely skilled to examine whether the intervention also reduces maladaptive behaviors such as drug abuse, violence, and suicide. Both self-directedness and mobility address barriers Veterans report with traditional treatments. Developing alternative treatments would also reduce dependence on pharmacological treatments, reduce the need for clinic visits, minimize associated stigma, and allow patients to feel actively engaged in their own treatment. Participants may also benefit personally from being in this research study by experiencing reduced pain symptoms.

Data Analysis & Statistical Considerations

After accounting for a 3-month attrition rate of 10%, our targeted sample of 300 (100 in each treatment arm) will have 80% power to detect an effect size equivalent to Cohen's $d = 0.42$. This corresponds closely to findings from a published clinical trial of neurofeedback to reduce chronic pain (Jensen et al., 2013), which found 3-month improvements in pain intensity (0-10 rating scale) equivalent to Cohen's $d = 0.38$. Unless otherwise specified, we will fit a mixed longitudinal model with change from baseline to 3 months and 6 months as the response variable, pain stratification group as a blocking factor, randomized treatment as the between-subjects factor, month as a within-subjects factor, the interaction between treatment and month, and baseline score as a covariate. We hypothesize Veterans in the two intervention groups will report less pain at 3 months compared to Veterans in the control group. We also hypothesize Veterans in the two intervention groups will show increased (8–12 Hz) alpha power on EEG at 3 months compared to Veterans in the control group.

Data & Safety Monitoring

Participants will be screened and excluded from study participation if they have epilepsy/seizure disorder. Potential participants will be asked about seizures twice prior to enrollment in the study intervention: once on the phone screen and again during the initial study interview. Participants will be told to discontinue the study intervention if they develop a seizure disorder or have a seizure. Participants will also be asked about seizures at weeks 1, 3, 6, 9, and 12 of study participation, and will be told to stop the intervention if they report one.

During study participation, participants will be asked about and monitored for all adverse reactions. Individual participants will be told to discontinue their use of the study intervention if they report a moderate or severe adverse determined to be possibly or very likely related to the study. These participants will be instructed to no longer practice the intervention for the duration of their participation, but will be given the opportunity to complete the rest of study data collection visits. Participants will also be routinely asked about suicidal ideation and violent ideation. Participants who report suicidal or homicidal ideation with a plan will be instructed to discontinue their use of the study intervention. We will be reporting every 6 months to an external Data Safety and Monitoring Board (DSMB) independent of the sponsor. The DSMB will monitor subject accrual (including participant withdrawal) and adverse events. They will also provide consultation on safety issues as needed throughout the study.

When a participant expresses suicidal or homicidal ideation, study staff will respond using a standard of practice that has been used successfully in other studies involving military veterans at Duke University (See “Duke specific Psychiatric Emergency SOP” document for the process, and the “Risk Screen Documentation” document for questions used for suicidal and homicidal ideation assessment). The study staff member responsible for the interaction with the participant will be instructed to gather more information from the participant, including information about suicidal plan, means, intent, and history of suicidal behavior. Based on participant’s responses and risk, study staff may respond in a number of ways including offering resources, asking about participant’s linkage to treatment, recommending further evaluation at the ER, initiating involuntary evaluation, or other responses deemed clinically appropriate. If the participant reports ideation over the phone, the participant will be informed that the PI may contact him/her to talk more about his/her thoughts. The study coordinator will obtain current contact information for the participant and inform the PI, who will contact the participant as necessary to ensure participant safety.

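### Does leaving the Aim 1 pain score, its mode and its order unstated open the 3-month comparison to assessor influence?

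*Combined protocol and SAP*

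**What the plan says.** Purpose of the Study states Aim 1 as a comparison of reported pain: "Veterans in the two intervention groups will report less pain at 3 months compared to Veterans in the control group". It names no instrument.

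Design & Procedures gives these sources of pain data:

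- Baseline: "clinical interviews for TBI, chronic pain, and cognitive function; self-report instruments measuring chronic pain".
- Follow-up at 12 and 24 weeks: "During both follow-up visits, veterans will complete clinical interview, pain assessment, self-report instruments".
- In the apps: "Participants will be asked to report their current level of pain, stress, and anger before and after each session".

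For remote follow-up, "participants will complete part of the visit over the phone and/or WebEx/Zoom, emailed a Qualtrics link to complete survey questionnaires". The same section has coordinators reinforce training and "observe participants utilizing the intervention in their home environment". Under the COVID-19 arrangements they also "will conduct baseline (screening/enrollment) follow-up interviews over the phone or via WebEx/Zoom, as needed". That wording is garbled but most likely covers both baseline and follow-up.

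Study Interventions has staff collect app-usage data at several contacts, including both follow-up visits. For remote participants, "Data will be downloaded from the iPods once they are shipped back to our Duke offices". The section presents a common device label as the blinding measure. It also describes apps matched in appearance, background sounds and schedule. No masked outcome assessor is described.

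Data Analysis & Statistical Considerations models change from baseline, adjusted for the baseline score and a pain stratification factor, again without naming an instrument. A 0-10 scale appears there for a cited trial, and in Selection of Subjects for eligibility.

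**The concern.** Aim 1 is subjective, and its hypothesis favours both active arms. If the analysed score is elicited by someone who has trained the participant and watched the app in use, or is given straight after talking to that person, the answer could drift towards the hypothesis. Baseline adjustment cannot remove such a shift, because it arises after randomisation and differs by arm.

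The text leaves room for this. The follow-up pain assessment has no stated mode and no baseline item of the same name. A remote visit is split between live contact and a survey link, and nothing says which side holds the pain score or which comes first. In the office, app-usage data are collected at the same visit with no stated order. The apparent remedy is to name the score and have it self-completed before any staff contact.

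**Working it through.** **1. The plan's own figure.** Inputs from Data Analysis & Statistical Considerations: 100 per arm, 10% attrition at 3 months, d = 0.42, power 80%. Alpha is not stated; two-sided 5% for one active arm against control is assumed.

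- n = 100 × 0.90 = 90 per arm.
- Noncentrality = 0.42 × √(90/2) = 0.42 × 6.708 = 2.817.
- Normal approximation: power = Φ(2.817 − 1.960) = Φ(0.857) = 80.4%. The t-test gives 80.0%.

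The stated 80% reproduces. Naming the score, its mode or its order would not alter it.

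**2. How much spurious shift would matter.** These are tolerances, not estimates of bias.

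- Smallest significant difference (t, 178 df): 1.973 × √(2/90) = 0.294 SD.
- Margin at the cited benchmark: 0.38 − 0.294 = 0.086 SD. This reads 0.38 as a between-arm difference, although the plan describes it only as improvement at 3 months.
- Margin at the planned effect: 0.42 − 0.294 = 0.126 SD.
- With no true effect, shifts of 0.05, 0.10 and 0.20 SD give rejection rates of 6.3%, 10.3% and 26.9% (normal approximation). A shift of 0.098 SD gives 10% by the t-test. For an assumed SD of 1.5 to 2.5 points, that is 0.147 to 0.245 points on a 0-10 scale.

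The planned model adjusts for baseline. With an assumed baseline correlation of 0.3 to 0.7, the 0.294 threshold is multiplied by √(1 − r²) and becomes about 0.28 to 0.21. The 0.086 margin becomes about 0.10 to 0.17, and the 0.098 shift about 0.09 to 0.07. One tolerance loosens and the other tightens. Nothing in these figures is specific to assessors; any bias at 90 per arm would give them.

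**3. Whether the conditions hold.**

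| Condition | What the documents show |
|---|---|
| Score elicited by staff, or given after an interview | Not stated. Aim 1 speaks of veterans reporting pain, self-report pain instruments exist at baseline, and remote questionnaires go by emailed link. |
| Those staff know the arm | Plausible for remote visits. Not established in the office, where the follow-up interviewer is not identified. |
| They push answers towards the hypothesis | Nothing either way. |

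**4. Which measures fit the model.** The response is change from baseline at 3 and 6 months, so the score must exist at all three times. In-app ratings accompany practice sessions, which start after the baseline assessment and are scheduled for 12 weeks only. They supply neither a pre-treatment baseline nor a scheduled 24-week value. The baseline pain interview is grouped with the TBI and cognitive interviews, which suits eligibility or description. A self-reported pain score is the natural reading.

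**5. What reordering would achieve.** Coordinator contacts are scheduled at weeks 1, 3, 6 and 9, all before the 12-week score. Remote participants are also asked for examples of when the intervention helped. Self-completion at the start of the 12-week visit removes same-day influence but not what those contacts have already done. Taking the pain score before the iPod data conceals nothing from a coordinator who already knows the arm, and in-person visits are no longer required.

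**The case for a change.** The strongest case drops the assessor and keeps the omission: an unnamed score allows a choice among measures after the data are seen. If every candidate were tested at two-sided 5% and any significant one reported, simulation with assumed correlations of 0.5 to 0.9 gives an error rate from 7.0% (two measures, correlation 0.9) to 15.6% (four measures, correlation 0.5). With two candidates, which is nearer the mark once the in-app ratings and the descriptive interview are set aside, the range is 7.0% to 9.1%.

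The gap stands, and a report of Aim 1 should say which score was intended, how it was collected and who was blinded. But that records a definition; it corrects no rule that gives a wrong answer. The documents do not show that a choice was made after seeing data, and this is a different matter from assessor influence.

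It is also fair that patient report does not settle mode, since a veteran can report pain to an interviewer or alone on a form. The matched apps do not close this: the headset is described only for the neurofeedback arm, and coordinators who watch sessions can tell the arms apart. So the risk cannot be called zero. Equally, self-completion before the visit would not make it zero, given the earlier contacts and the participants' own expectations.

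**Conclusion.** No change to the plan. The score, mode and order are indeed unstated, but the route to bias is a chain of conditions that the documents do not establish, and the text leans towards the reading on which the risk is small. Its size in this trial cannot be derived. The tolerances (0.086 and 0.126 SD of margin; 0.098 SD to double the error rate) are generic and assume 90 per arm, a two-sided 5% level per comparison and an unadjusted t-test. Sample size, power and model are untouched.

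Changing visit order or mode now is a debatable trade. The document is dated December 2022 and already carries the COVID-19 adaptations. A switch could make follow-up differ from baseline, and later visits from earlier ones, for a benefit limited to same-day influence.

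The conclusion rests on the Aim 1 score being a patient-reported measure available at baseline and both follow-ups. If the intended score proved to be one that coordinators who know the arm elicit in conversation, assessor influence would deserve a fresh look.
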